6.8 Treatment Compliance

Study drug accountability was to be performed on an ongoing basis by the study staff and checked by the monitor during site visits and at the completion of the study. Subjects were asked to return all unused study drug as well as the empty packages at each visit. The study coordinator or designee will document the unused study drug and verify that the quantity is consistent with the intended dosing schedule. If non-compliance is suspected, the clinical site personnel will re-educate the subject on the importance of proper adherence to the prescribed dosing. Continued non-compliance may lead to termination of the subject from the study after consultation between the Investigator and the Sponsor. Treatment compliance will be presented by two analyses: by analysis of IMP pill count data and IMP dosing as reported during the study.

6.8.1 Analysis of Pill Count Data

Coupled with the typical issues of lost and irretrievable IMP tablets, the protocol allowed that a subject could dose adjust during the study, a dose interruption could occur if medically warranted, and subjects were asked to remain on study (on or off IMP) pending adjudication of the primary clinical worsening event, pill count data will not provide an absolutely accurate compliance measurement. The following will be calculated:

- the number of tablets dispensed during the study (Baseline Visit through End of Study Visit)
- the number of tablets returned during the study
- the number of used tablets (calculated as tablets dispensed minus tablets returned)
- the duration of exposure (see Section 7.1)
- the number of expected pills taken at 15 µg and 30 µg QID
- percent of used tablets for number of expected pills for 15 µg and 30 µg QID overall and by 20% increments

Descriptive statistics will be presented by treatment group and subgroups, including, but not limited to, age, sex, racial, country, PAH etiology, background PAH therapy, background inhaled treprostinil, baseline WHO (see Sections 6.7.1 and 6.7.2).

6.8.2 IMP Dosing

Sites were not required to record each dose of IMP taken during the study but IMP dosing was to be reported on the eCRF for first and last IMP dose as well as any doses taken while on site, any missed doses and any dose modification. The subjects are to receive QID dosing of IMP with some titration (see protocol). Three different summaries of compliance to IMP will be reported:

Summary of Daily Dosing

The first summary will measure if any of the 4 doses to be taken on a given day is taken than the subject is compliant for that day. The following will be calculated:

- the number of minimally compliant days [≥ 1 of QID doses taken during the study (Baseline Visit through End of Study Visit)]
- the duration of exposure (see Section 7.1)
- percent of minimally compliant days (as divided by duration of exposure) overall and by 20% increments

Summary of QID Dosing

The second summary will measure if all of the 4 doses to be taken on a given day are taken than the subject is compliant for that day. The following will be calculated:

- the number of maximally compliant days [all of QID doses taken during the study (Baseline Visit through End of Study Visit)]
- the duration of exposure (see Section 7.1)
- percent of maximally compliant days (as divided by duration of exposure) overall and by 20% increments

Summaries of IMP and Inhaled Treprostинil Dosing

The plan for administration of drug in this study was predicated on the hypothesis that dual dosing, hitting the receptors in two different ways at the same time, is beneficial. To measure the extent to which the dosing of IMP and inhaled treprostинil was performed nearly simultaneously, the two treatment groups will be compared with respect to the frequency of times dosing with IMP and inhaled treprostинil not separated by more than (a) 5 minutes and (b) 10 minutes.

Descriptive statistics will be presented by treatment group and subgroups, including, but not limited to, age, sex, racial, country, PAH etiology, background PAH therapy, background inhaled treprostинil, baseline WHO (see Sections 6.7.1 and 6.7.2). Other analyses may be performed as suggested by the data. Analogous summaries will be presented for use of inhaled treprostинil.

6.9 Analysis of Efficacy

All statistical analyses of efficacy will include the stratification variable, baseline inhaled treprostinil use, as a covariate. The sections that describe the analysis of the other secondary outcomes list other planned covariates.

Because the number of subjects in each investigational site is expected to be small, site will not be used as a covariate in the analyses. Moreover, no pooling algorithm will be used.

6.10 Hypothesis Testing

A three-stage process of hypothesis testing will be employed to control for the multiplicity of secondary endpoints.

6.10.1 Stage 1: Testing for Primary Endpoint

If, at a two-sided alpha level of 0.05, the comparison of esuberaprost to placebo on the primary endpoint, TtCW,

- is significant, then hypothesis testing will continue to Stage 2.
- is *not* significant, then formal hypothesis testing will stop.

6.10.2 Stage 2: Testing the Key Secondary Endpoints

Stage 2 hypothesis testing will employ the Simes' procedure for control of multiplicity (Simes, 1986). Testing in this stage will be at a two-sided Type I error rate of 0.05 for the three secondary endpoints:

- The comparison of esuberaprost to placebo on baseline-adjusted change from baseline 6MWT at Week 24
- The comparison of esuberaprost to placebo on TtCF
- The comparison of esuberaprost to placebo on worsening from baseline in WHO Functional Class at Week 24

Hypothesis testing will continue to Stage 3 only if at least one of the comparisons of esuberaprost to placebo on these endpoints is significant by the Simes' procedure. The Simes' procedure's critical value from the final significant test in Stage 2 will be carried forward and used for the critical value in Stage 3.

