Hypothesis testing of secondary efficacy endpoints may be conducted using a gatekeeper strategy such that any secondary endpoints will be considered for statistical significance only if the primary endpoint is statistically significant. Under closed testing procedures, the type I family-wise error rate will be controlled at the 0.05 level of significance. The SAP will detail the order of testing for secondary efficacy endpoints.

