6.10.3 Stage 3: Testing for Other Secondary Endpoints

Stage 3 hypothesis testing will employ simple hierarchical testing on the pre-specified endpoints listed in Section 5.1.3. Testing in this stage will be performed at the final Simes' procedure's critical value carried forward from Stage 2.

If any comparison of esuberaprost to placebo is not significant at the critical value carried forward from Stage 2, then formal testing will stop.

As described in Section 5.1.3, endpoints in Stage 3 will be reviewed at the time of the Blinded Data Review (see Section 6.11) and the order of testing will be determined on the basis of clinical importance and likely statistical power. The order will be designed to protect Type I error rate.

Statistical analyses for exploratory endpoints not otherwise predefined for hypothesis testing will be presented as point estimates with associated 95% CIs.

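### Carrying the last Stage 2 critical value into Stage 3 after a partial success lets the family-wise error reach about 8%, against the 5% promised

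*SAP*

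**What the plan says.** SAP 6.10 sets out three stages. Stage 1 tests time to clinical worsening at two-sided 0.05, and formal testing stops if it fails.

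Stage 2 (SAP 6.10.2) covers change in 6MWT at Week 24, time to clinical failure, and worsening of WHO Functional Class at Week 24. It uses the Simes procedure: "Testing in this stage will be at a two-sided Type I error rate of 0.05 for the three secondary endpoints". The ordered cut-offs are not written out. Testing goes on to Stage 3 "only if at least one of the comparisons of esuberaprost to placebo on these endpoints is significant". The level for Stage 3 is then fixed by the rule that the "critical value from the final significant test in Stage 2 will be carried forward and used for the critical value in Stage 3".

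Stage 3 (SAP 6.10.3) is a fixed-order hierarchy in which every test is made at the "critical value carried forward from Stage 2".

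On the error rate, Protocol 10.9 states that "the type I family-wise error rate will be controlled at the 0.05 level of significance". Protocol 10.1 repeats this and, for labelling, caps the experiment-wise error at 5%. SAP 5.1 and 6.10 give control of type I error and of multiplicity as the purpose of the staged testing.

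**The concern.** There are two separate faults.

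1. **Simes is a test of the global null.** It asks whether any of the three effects exists. If its ordered cut-offs are used step-up to claim individual endpoints, one endpoint with a real effect takes the smallest cut-off. The remaining null endpoints are then compared with 0.0333 and 0.05, which is too generous for two nulls.

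2. **Stage 3 receives alpha that Stage 2 has not released.** When only one or two Stage 2 endpoints succeed, the failed ones have already used the full 0.05 between them. Testing Stage 3 at a further 0.0167 or 0.0333 adds to that.

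At stake are the secondary claims made after a positive primary result, which is what the labelling sentence in Protocol 10.1 covers. The pattern that causes the inflation, real effects on some key secondaries but not all, is a natural one here. Time to clinical failure contains every confirmed clinical worsening event, so a real primary effect probably carries over to it and need not carry over to the other two.

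**Working it through.** **Inputs.** Stage 2 level 0.05 with three endpoints, and one success opens Stage 3 (SAP 6.10.2). The Stage 3 level is the last Stage 2 critical value (SAP 6.10.2 and 6.10.3). The target is 0.05 (Protocol 10.1 and 10.9). *Assumptions:* the standard Simes cut-offs i × 0.05/3 = 0.0167, 0.0333, 0.05; a true primary effect, so that Stage 1 is passed; real Stage 2 effects strong enough to be always detected; and a null first endpoint in Stage 3. Because Stage 3 is a fixed sequence, a null first endpoint is enough to give its error.

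**Where 5% is reproduced.** With no real Stage 2 effect, the Simes global test gives 0.050, and any entry to Stage 3 already follows a false claim. With three real effects, the carried value is 0.05 and Stage 3 gives 0.050.

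**One real effect, two nulls (independent).** Stage 2 makes no false claim if both null p-values exceed 0.0333 and they are not both at or below 0.05:

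- Stage 2 error = 1 − [(1 − 0.0333)² − 0.0167²] = 0.0658
- Stage 3 at 0.0167 adds 0.9342 × 0.0167 = 0.0156
- Total = 0.0814

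**Two real effects, one null (independent).** The null is tested at 0.05. If it fails, Stage 3 is tested at 0.0333:

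- Total = 0.05 + 0.95 × 0.0333 = 0.0817

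Multiplying by the 97% power that SAP 4.1 gives for the primary test at 0.05: 0.97 × 0.0817 = 0.079.

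**Hochberg reading (0.0167, 0.025, 0.05; independent).**

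- One real effect: Stage 2 error = 1 − [(1 − 0.025)² − 0.025²] = 0.050. Total = 0.05 + 0.95 × 0.0167 = 0.0658
- Two real effects: 0.05 + 0.95 × 0.025 = 0.0738

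**Correlated endpoints.** Simulation with 2,000,000 draws per case, equal correlation and strong real effects:

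| Cut-offs | Real Stage 2 effects | ρ = 0 | 0.3 | 0.5 | 0.7 | 0.9 |
|---|---|---|---|---|---|---|
| Simes | 1 | 8.1% | 7.9% | 7.3% | 6.5% | 5.2% |
| Simes | 2 | 8.2% | 8.0% | 7.7% | 7.1% | 6.0% |
| Hochberg | 1 | 6.6% | 6.4% | 6.0% | 5.4% | 4.4% |
| Hochberg | 2 | 7.4% | 7.2% | 7.0% | 6.5% | 5.6% |

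**Moderate real effects.** The table gives the highest error over 0 to 3 real effects, with each real endpoint given 90% or 80% power at 0.05 (an assumption, since the documents give no power for these endpoints):

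| Cut-offs | Power | ρ = 0 | 0.5 | 0.7 |
|---|---|---|---|---|
| Simes | 90% | 7.4% | 6.2% | 5.3% |
| Simes | 80% | 6.8% | 5.8% | 5.0% |
| Hochberg | 90% | 6.6% | 5.6% | below 5% |
| Hochberg | 80% | 5.9% | below 5% | below 5% |

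**The case against.** The strongest reply is that the cut-offs are assumed. The SAP names Simes without listing them, and the protocol sentence that promises 5% also refers to closed testing. Simes tests inside a closed procedure give Hommel, of which Hochberg is a simpler conservative form. Both control Stage 2 at 5% for independent or positively dependent tests. On that reading the first fault goes, and what is left of it is a need to name the procedure. The second fault stays: the Hochberg rows exceed 5% because of the carry-forward alone.

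It is also fair that 8% is a limiting case. It needs low correlation, one or two effects that are almost certain to be detected, and exact nulls elsewhere. Time to clinical failure is built partly from walk distance and functional class, so the three endpoints are unlikely to be independent. The practical excess is often 0 to 2 points. Even so, family-wise control is judged at its worst configuration, and moderate correlation does not restore 5% when the real effects are strong.

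Two further points narrow the concern without removing it. Neither document uses the word strong for the control promised, the protocol says only that gatekeeping may be used, and the SAP states that it supersedes the protocol's statistical text. But the SAP sets the same aim for its own scheme. And the primary conclusion is untouched, because Stage 1 is a plain 0.05 gate.

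SAP 6.10.3 says the Stage 3 order will be chosen to protect the type I error. Ordering cannot repair an entry level that is already too high.

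**Conclusion.** The concern holds. As written, the staged procedure does not control the family-wise error at 5%. The worst case found is 8.2% with Simes cut-offs and 7.4% with Hochberg cut-offs, both under independence with strong real effects on two of the three key secondary endpoints. The Simes figure is about 1.6 times the promised rate (0.0817/0.05). Positive correlation and weaker effects lower the excess and can remove it. The 5% figure is assured only when none or all of the Stage 2 effects are real. The inflation affects Stage 2 and Stage 3 claims after a positive primary result, and not the primary test itself. The rule should be corrected before unblinding, because a change to the testing scheme after that would not be credible.

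**What to change.** - Name the Stage 2 procedure as Hochberg (or Hommel) at two-sided 0.05 and write out how it decides each endpoint. For Hochberg the cut-offs are 0.0167, 0.025 and 0.05.
- Open Stage 3, in fixed order at 0.05, only if all three key secondary endpoints are rejected.
- Delete the carry-forward sentences in SAP 6.10.2 and 6.10.3.

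This works by construction. If any Stage 2 null is true, Stage 3 can open only after a false Stage 2 claim, so the total error equals the Stage 2 error. If none is true, Stage 3 runs at 0.05. In simulation the error was at most 0.050, within simulation error, in every configuration and correlation tried.

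If the sponsor wants Stage 3 to open after a partial success, a truncated Hochberg gatekeeper is a valid alternative. Its truncation fraction must then be stated in the SAP, since it decides how much alpha Stage 2 gives up and how much reaches Stage 3.

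The cost is SAP wording only, and it can go into a SAP revision or addendum before unblinding. The price is that Stage 3 opens less often, and under Hochberg the middle cut-off falls from 0.0333 to 0.025.

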6.10.3 Stage 3: Testing for Other Secondary Endpoints

Stage 3 hypothesis testing will employ simple hierarchical testing on the pre-specified endpoints listed in Section 5.1.3. Testing in this stage will be performed at the final Simes' procedure's critical value carried forward from Stage 2.

If any comparison of esuberaprost to placebo is not significant at the critical value carried forward from Stage 2, then formal testing will stop.

As described in Section 5.1.3, endpoints in Stage 3 will be reviewed at the time of the Blinded Data Review (see Section 6.11) and the order of testing will be determined on the basis of clinical importance and likely statistical power. The order will be designed to protect Type I error rate.

Statistical analyses for exploratory endpoints not otherwise predefined for hypothesis testing will be presented as point estimates with associated 95% CIs.

6.12 Primary Efficacy Analysis

As described in Section 2.1, the primary efficacy outcome is the TtCW, measured in days, where clinical worsening is defined as the first occurrence of any of the following:

- Death (all causes)
- Hospitalization due to worsening PAH
- Initiation of a parenteral (infusion or sub-cutaneous) prostacyclin directly related to worsening PAH
- Disease progression

- Unsatisfactory long-term clinical response

As described above, a blinded Event Adjudication Committee (EAC) will review all suspected clinical worsening events and make a final determination for each (see [Appendix 1](#)). The EAC Charter, Version [REDACTED], specifies evidence to be provided to the EAC along with the general rules and criteria for EAC confirmation of a primary endpoint of clinical worsening. Because the EAC Charter cannot address every possible scenario, the EAC Charter shall be viewed as a framework under which the EAC will operate. Each case will be determined on the basis of a consensus of the EAC, the members of whom are independent experts in PAH. Please see [Appendix 2](#) for general rules and criteria excerpted from the EAC Charter.

Subjects were not required to discontinue from the study after meeting a primary endpoint; thus, more than one clinical worsening event may be reported for the same subject. This section defines the calculation of time to each component of the primary outcome. The protocol specifies that investigators follow each subject for 30 days after the subject discontinues from the study to assess the occurrence of SAEs and for 90 days after the subject stops study medication for vital status. Further, the investigators are instructed to provide all clinical worsening events that occur after the primary clinical worsening event, as well as the vital status of all subjects at the time the sponsor terminates the study.

6.12.1 Death (All Cause)

Deaths that occur at any time from randomization to 90 days after the subject's last study visit is counted as a death for the primary efficacy analysis. All those still alive 90 days after their last visit are censored for death at the 90 day time even if it is known that they died after the 90 day window.

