2 STUDY OBJECTIVES

2.1 **Primary Objective**

The primary objective of this study is to compare the effect of BPS-314*d*-MR versus placebo added to treprostinil, inhaled (Tyvaso®) on the composite endpoint of time-to-clinical-worsening (TtCW), defined as the time from randomization to the first of any of the following clinical worsening events:

- Death (all causes)
- Hospitalization due to worsening PAH defined as:
 - Non-elective hospitalization lasting at least 24 hours in duration caused by clinical conditions directly related to PAH and/or right heart failure and requiring intensification of treatment; or
 - Lung or heart / lung transplantation; or
 - Atrial septostomy
- Initiation of a parenteral (infusion or sub-cutaneous) prostacyclin, directly related to worsening PAH (transient use [≤ 7 days] for non-PAH related illness allowable)
- Disease progression (all criteria required):
 - A decrease in six minute walk distance (6MWD) of at least 15% from Baseline (defined as the average of the two 6MWTs performed on sequential days of the Baseline Visit), or being too ill to walk as a consequence of PAH progression, confirmed by six-minute walk tests (6MWT) performed at 2 consecutive visits
 - Worsening of PAH symptoms, which must include either:
 - An increase in WHO Functional Class or
 - Worsening symptoms of right heart failure
- Unsatisfactory long-term clinical response (all criteria below required):
 - Receiving randomized treatment for at least 24 weeks
 - A decrease of at least 15% from Baseline (defined as the average of the two Baseline Visit 6MWTs) in 6MWD, or too ill to walk, directly related to PAH progression, at Week 24 and beyond; at 2 consecutive visits, and
 - Sustained WHO Functional Class III or IV symptoms for at least 24 weeks.

The Investigator will initially judge whether a suspected clinical worsening event has occurred based on the definition provided above. An Event Adjudication Committee (EAC) will review all suspected clinical worsening events and make a final determination. The EAC will be composed of medical experts in the PAH field, will be independent from the Sponsor, and will assess each event in a blinded fashion. Specific details regarding the Committee's membership, processes and procedures will be outlined in the EAC charter.

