Subjects will continue participation in the study until it is formally concluded by the Sponsor. Subjects are expected to remain on study drug throughout their participation in the study unless/until IV or SQ prostanoid therapy is added or in the event of lung transplantation. If a subject discontinues the study for any reason prior to the formal conclusion of the study by the Sponsor, the subject will be asked to return to the clinical for an End of Study (Early Termination) Visit. Vital status will be assessed for all randomized subjects at the formal conclusion of the study. For randomized subjects who terminate early, vital status will be assessed three months following discontinuation unless the formal conclusion of the study occurs within the three month time period.

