Vital status will be assessed for all randomized subjects at the formal conclusion of the study. For randomized subjects who terminate early, vital status will be assessed three months following discontinuation unless the formal conclusion of the study occurs within the three month time period. Study site personnel will record vital status information in source documents and record relevant information on appropriate CRFs.

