10.3 Analysis Populations

With the exception of the assessment of vital status until the formal close of the study, the statistical analyses or summaries for efficacy and safety parameters will include evaluations performed from randomization up to the date of the subject's last study visit or 30 days after the permanent discontinuation of study drug. Any additional evaluations will be included in the data listings only.

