6.4.2 Handling of Missing Data

The sponsor acknowledges the implications of missing data on the integrity of study outcomes and, consistent with Fleming's recommendations (2011), implemented the following strategies to minimize the extent of missing data:

1. All subjects were allowed to continue in the study until the close of study, whether on IMP or not. Subjects were not to be summarily discontinued from the study, unless 1) the subject withdrew informed consent; 2) the subject met a primary endpoint and declined continuation in the study; or 3) the subject continued to be non-adherent to study protocol after repeated attempts to correct (at least 6 months). However, the subject has the right to discontinue from the study at any time. All subjects who discontinue the study, unless they withdraw informed consent, will continue to be followed, to the extent possible, for vital status until the sponsor concludes the study.
2. Recent publications (Sitbon et al., 2015; Galiè et al., 2015) have shown that roughly 20% of subjects prematurely terminate from mortality and morbidity studies in PAH. The sponsor has throughout the study engaged with study investigators to encourage subjects' retention in the study, adherence with the protocol, and compliance with IMP.
3. While the study protocol is necessarily complex in order to obtain the scientific data to evaluate the safety and efficacy of the IMP, the sponsor designed the protocol in the manner that was not burdensome to the subjects: 1) Much of the data collected for secondary endpoints is derived from assessments performed for 'standard of care' visits; 2) Study visits are minimal (quarterly) with permissive visit windows (\pm 10 days); 3) Use of optional substudies for exploratory endpoints; and 4) Sponsor-provided Tyvaso to all subjects in the study.

Methods for handling missing data will be described in the sections discussing each outcome.

No imputation is planned for missing safety or exploratory data.

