6.14.5 Total Mortality

Vital status will be assessed for each randomized subject through the end of the study. All subjects who discontinue the study, either for premature termination or for meeting a primary endpoint of clinical worsening, will continue to be followed, to the extent possible, for vital status until the sponsor concludes the study. Subjects who are lost to follow-up will be censored at the date known alive. The total mortality (all cause death) in the two treatment groups will be evaluated with a Cox regression analysis to provide an estimated hazard ratio and corresponding 95% CI.

Time-to-death analyses will use the following SAS code with different rules for the variable *status(0)*.

```
proc lifetest data= set plots=survival;
  time TtCW * status(0);
  strata treprostinil_use / group=treatment test=logrank;
  run;
```

Deaths are categorized as Cardiovascular related, PAH related, and other. A table will show the proportion of deaths, by treatment arm, in each category. Sensitivity analyses for this table will be described in an addendum to this SAP, which will be completed after the Blind Data Review.

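### SAP 6.12.1 censors deaths known to have occurred more than 90 days after the last visit, and no named sensitivity analysis of the primary endpoint tests whether that matters

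*SAP*

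**What the plan says.** - **Endpoint.** Protocol 2.1 and SAP 2.1 define TtCW as time from randomization to the first of several events. Death from any cause is listed without a time limit.
- **Protocol, vital status.** Section 2.1, repeated in 7.14: "Vital status will be assessed for all randomized subjects at the formal conclusion of the study". The next sentence adds an intermediate check: "For randomized subjects who terminate early, vital status will be assessed three months following discontinuation", unless the study closes first. Section 10.3 limits efficacy and safety data to the last study visit or 30 days after study drug stops, but opens "With the exception of the assessment of vital status until the formal close of the study".
- **SAP, vital status.** Under 6.14.5, subjects who discontinue "will continue to be followed, to the extent possible, for vital status until the sponsor concludes the study". Section 6.4.2 says the same, except for those who withdraw consent.
- **SAP, primary analysis.** Section 6.12.1 counts deaths up to 90 days after the last study visit. For survivors at that point it says: "All those still alive 90 days after their last visit are censored for death at the 90 day time even if it is known". The rest of that sentence refers to deaths falling after the window.
- **SAP, sensitivity analyses.** Section 6.12.8 names two: censoring when study medication stops, and a series censoring on each of Days 1 to 90 afterwards. It allows others to be added by addendum before database lock.

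**The concern.** Death is the hardest component of the composite and the one the plan undertakes to follow after a subject leaves. Setting aside known deaths does no harm if leaving is unrelated to prognosis. It can mislead if subjects in one arm leave because they are deteriorating and then die. The usual safeguard is a sensitivity analysis that puts those deaths back. Here both named analyses go the other way and shorten follow-up. If the TtCW result were close to the significance boundary, a reader of the study report would have no prespecified TtCW result showing whether it depended on the 90-day limit.

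**Working it through.** **1. Design figures reproduce.** The one-year rates of 25% and 45% (SAP 4.1) give HR = ln 0.75 / ln 0.55 = 0.481. Schoenfeld's formula at two-sided 0.01 and 90% power gives 4 × (2.576 + 1.282)² / (ln 0.481)² = 112 events, against 113 stated. Power with 113 events at 0.05 is 97.3%, against 97% stated. An exponential test with 1.5 years' accrual and 2.5 years in total needs 116 per arm, as the protocol says. The point does not dispute any of these.

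**2. Which deaths are affected.** A death is set aside only if the subject had no earlier component event, left the study, died more than 90 days after the last visit and before study close, and the death is known.

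**3. How many.** The documents give no count, so these inputs are assumptions:
- Early termination of 20%. SAP 6.4.2 notes that recent publications "have shown that roughly 20% of subjects prematurely terminate from mortality and morbidity studies in PAH". Applied to 240 subjects this is 48 leavers.
- Annual mortality of 15%, borrowed from the first-year-after-diagnosis figure in Protocol 1.1. The hazard is h = −ln 0.85 = 0.1625 per year.
- T years from day 90 to study close.

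Deaths outside the window = 48 × exp(−0.25h) × (1 − exp(−hT)) = 46.1 × (1 − exp(−0.1625T)).

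| T (years) | Deaths | Share of 113 |
|---|---|---|
| 0.5 | 3.6 | 3% |
| 1 | 6.9 | 6% |
| 2 | 12.8 | 11% |

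With termination of 10% to 30% and mortality of 5% to 25%, the range is 0.6 to 29. All are upper figures, because the 48 include subjects with an earlier TtCW event and subjects who withdrew consent.

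**4. Could it change a result?** Take an observed HR of 0.65 on 113 events. By the Peto approximation, V = 113/4 = 28.25, O − E = ln 0.65 × 28.25 = −12.17, and p = 0.022. Add 7 deaths, so V = 120/4 = 30. With half of those at risk on active, O − E changes by 7 × (active share − 0.5).

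| Split of the 7 deaths | O − E | HR | p |
|---|---|---|---|
| All active | −8.67 | 0.749 | 0.11 |
| 2:1 active | −11.00 | 0.693 | 0.045 |
| Even | −12.17 | 0.667 | 0.026 |
| 2:1 placebo | −13.34 | 0.641 | 0.015 |
| All placebo | −15.67 | 0.593 | 0.004 |

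A moderate result is at risk only if the deaths are markedly unbalanced, and the shift can go either way.

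**5. At the design effect, with follow-up time included.** At the design event probabilities (0.391 active, 0.637 placebo), 113 events split about 43 to 70. Person-years are 43/0.2877 = 149.5 and 70/0.5978 = 117.1. Suppose 32 leavers are on active and 16 on placebo, with 15% mortality over one further year. That adds 4.8 and 2.4 deaths, and 32 × 0.923 = 29.5 and 16 × 0.923 = 14.8 person-years, where 0.923 = 0.15/0.1625. The HR is (47.8/179.0) / (72.4/131.9) = 0.486. With 24 leavers per arm it is (46.6/171.6) / (73.6/139.2) = 0.514, which is dilution rather than removal of bias.

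**The case against.** The strongest defence is that the 90 days is not arbitrary. It matches the protocol's three-month check for early terminators, and one common window treats leavers alike. Protocol 10.3 exempts vital status from a cut-off but does not say that every death up to study close is a TtCW event. Protocol section 10 and SAP section 1 let the SAP settle methods. The late deaths are reported in total mortality, and SAP 6.12.6 and 6.12.8 provide for addenda before unblinding or database lock. All of this stands, and it supports keeping the 90-day rule as primary. It does not fill the gap: total mortality is a different endpoint, formally tested only after success in Stages 1 and 2, and an optional addendum is not a planned analysis.

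A reader might also infer stronger points that the documents do not support:
- **That these subjects are scored as event-free.** They are censored, which removes them from the risk set.
- **That the rule favours the arm losing more subjects.** That requires informative leaving, for which neither document gives a figure.
- **That the HR moves from 0.48 to 0.52.** Adding deaths alone gives 0.481 × (47.8/43) / (72.4/70) = 0.517. This omits the leavers' added follow-up; with it the result is 0.486.
- **That power is lost.** The trial runs until 113 events, so uncounted deaths do not lower that target.
- **That the primary rule breaches the protocol.** That is one reading of 10.3. The three-month sentence allows another, although it follows directly on the requirement for all randomized subjects and is more naturally an additional check.

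**Conclusion.** The point holds as a gap in the sensitivity analyses, not as an error in the primary rule. Deaths that the plan undertakes to ascertain are excluded from TtCW after 90 days, and neither named analysis examines the consequence. About 4 to 13 deaths could be involved at 20% early termination and 15% annual mortality. Both rates are borrowed from outside this trial, and the count is an upper figure. At the design effect the HR would stay near 0.49 to 0.51 under the two leaver splits worked above. A result near the significance boundary could change if late deaths were unbalanced, in a direction that cannot be known in advance. Follow-up for vital status is only as complete as sites can achieve, so the added analysis reduces the uncertainty about leavers without removing it.

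**What to change.** Add to SAP 6.12.8, or to the addendum it foresees before database lock, a TtCW analysis on all randomized subjects. Any death known on or before formal study close is an event if no earlier component event occurred. Leavers known to be alive are censored at the last date known alive. Use the same stratified log-rank test and Cox model, and tabulate by arm the deaths this adds.

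At the same time, reconcile two details of the window. The introduction to 6.12 counts 90 days from stopping study medication, whereas 6.12.1 counts from the last study visit. Section 6.12.6 censors subjects with no event at the last visit, so deaths count in a period in which survivors contribute no time.

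The cost is SAP wording and one more run, since the dates are already collected for total mortality. The drawback is that after exit only death is observed, not non-fatal worsening, which dilutes the effect somewhat. The analysis should therefore be reported beside the 90-day primary analysis and should not replace it.
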